7.4 Definition of End of Study

The end of study is after the last of the groups has finished their transfer test in the second week. Any participant, who hasn't shown at any of the teaching days, will be considered as having dropped out of trial.

8. Statistics and Analysis

8.1 Description of Statistical Methods

To examine the effects of guided-discovery-learning contra traditional instructional learning, the following outcomes will be measured:

- Difference in OSATS scores between the control and intervention groups far-transfer-test
- Difference in OSATS scores between the control and intervention groups near-transfer-test
- Difference in OSATS scores between the groups post-test.
- Difference in OSATS scores between the groups development from post-test to transfer-test.

To establish whether there is a significant level of difference in the above-mentioned measurements, students t-test will be used. A statistical software package will be used to calculate these (SPSS vs. 25.0, Chicago, IL).

Analysis

Analysis of the experimental data will be through a mixed-effects linear models with participants as random and instructional condition as fixed factors. We will conduct separate analysis for each hypothesis. For hypothesis 1, we will analyze post-test and near-transfer test scores through a multivariate model (repeated MANOVA or similar depending on model fit and sampling adequacy)¹⁸ with the expectation of a significant interaction indicating differences between groups at near-transfer but not on post-test. To address hypothesis 2, we will analyze performance on the vertical mattress suture using a univariate model (ANOVA). Where appropriate, covariates for performance such as post-test performance will be included to account for individual skill difference and to increase statistical power. A mixed-effects model will also compare participants' near- and far-transfer test scores across both conditions.

The qualitative data analysis is described in more detail in the additional protocol

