Primary outcome: To examine the effect of Guided-discovery-learning on far transfer of simple surgical skills	Difference in the two groups OSATS-scores on a far-transfer test evaluated by blinded raters
Secondary outcome: To examine the effect of Guided-discovery-learning on near-transfer of simple surgical skills To examine the primary learning-efficiency of the two types of teaching. To examine the effects on the different types of transfer for the intervention and control groups.	Difference in the two groups OSATS-scores on a near-transfer test evaluated by blinded raters Difference in OSATS-scores between immediate post-test. Difference in OSATS-scores between near-transfer and far-transfer-tests.
Explorative outcomes: To examine the difference in interaction between students receiving Guided-discovery, and those that didn't. To examine the difference in student interaction and approach to the task.	Using whole-room angle video recordings to observe the student-teacher interactions. Using task-focused video recordings to observe student-task interaction.
To examine different explorative approaches for examining the mechanics behind Guided-discovery To examine how students experienced the training.	Using think aloud video-recordings for select students. Using focus group interviews

5. Study Design

The study is a randomized experimental study comparing guided-discovery-learning to traditional instructional learning. The study will be performed at CAMES, including n=64 pre-clinical students from the Medical Faculty of Copenhagen University. Part 1 of this study is an experimental design with two phases that will test the efficacy of guided discovery: Phase 1 will be a learning phase with the experimental manipulations, and Phase 2 will take place one week later and be outcome assessment for near- and far transfer. Part 2 of this study will be an observational analysis of films of a sub-set of participants in the DD and IP conditions in order to establish differences in learning behaviors

between both conditions and possible mechanisms for guided-discovery learning. The analysis will compare how participants interact with the task in each learning condition including documenting activities in each phase and interactions with instructors.

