8.2 The Number of Participants

Learners:

We will recruit n=64 pre-clinical students from the Medical Faculty of Copenhagen University. We are targeting undergraduate students, rather than surgical residents, because we want novice learners, and we believe it is worthwhile to establish efficacy of our intervention group using simpler tasks which can be feasibly studied. We based our sample size on the previous pilot-study which suggests that detecting a large effect on a global rating scale (Hedges g of >0. with an alpha of 0.05 and power of 80% requires at least 13 participants per group with additional participants recruited for potential loss to follow-up²⁴ for a total of 16 per group. Participants will receive a certificate showing completed suturing course, as an honorarium to compensate for their time in the study.

Instructor and Raters:

We will recruit one 2nd year post-graduate surgical trainees to serve as an instructor. We will recruit an instructor who has some experience in teaching or coaching undergraduate students. Additionally, participant performance on the post-

and transfer tasks will be assessed by a blinded rater who will receive video-tapes of all relevant participant performances.

9. Data management

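### Near transfer has two unranked analyses in section 8.1 that answer different questions; if significance on either counted, the error rate would be about 8-10%

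*Combined protocol and SAP*

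**What the plan says.** Section 4 lists near transfer as the first secondary outcome, measured as "Difference in the two groups OSATS-scores on a near-transfer test evaluated by blinded raters". Far transfer is primary.

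Section 8.1 treats near transfer in two places:

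- **The list of measures.** The second item is "Difference in OSATS scores between the control and intervention groups near-transfer-test", and for all four listed items "students t-test will be used". The fourth item is the between-group difference in development from post-test to transfer test.
- **The Analysis paragraph.** Near-transfer and post-test scores are modelled together by a "repeated MANOVA or similar depending on model fit and sampling adequacy". The authors expect a significant interaction, with the groups differing at near transfer but not at post-test. A later sentence lets post-test performance enter as a covariate where appropriate.

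No sentence ranks these analyses, names the deciding one or gives a multiplicity rule.

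Three other parts of the plan bear on the point. Section 5 has each student place two sutures per test and promises a repeated-measures analysis for the multiple attempts. Section 7.3 assigns the teaching method to eight whole groups (eight students each, per section 5), and then each group to near or far transfer. The models in 8.1 have participants, but not teaching groups, as random.

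**The concern.** One declared outcome has two planned tests, and the second comes from a model family left open until fit is seen. The tests target different quantities. If DD led by the same amount at post-test and near transfer, the t-test could be significant while the interaction was null. If DD were slightly behind at post-test and slightly ahead at near transfer, the reverse could happen. The plan does not say which result would then stand as the near-transfer finding.

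Two things are at stake: which question the near-transfer claim answers, and whether the 5% level applies to it. The hypothesis numbering adds to this. Sections 3 and 5 tie hypothesis 1 to learning the new vertical mattress suture and hypothesis 2 to the near-transfer task. Section 8.1 analyses near transfer under hypothesis 1 and the vertical mattress suture under hypothesis 2. Until these are reconciled, the near-transfer interaction could be read as the test of the lead hypothesis.

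**Working it through.** **Plan's own figure.** The documents give no false-positive rate for near transfer, so there is none to reproduce. The sample-size statement supplies only alpha and the cell size.

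**Inputs**

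- Alpha 0.05, from section 8.2: "with an alpha of 0.05 and power of 80% requires at least 13 participants per group". Sidedness is not stated; two-sided is assumed.
- Students per arm at near transfer: 16 recruited ("for a total of 16 per group"; 4 cells × 16 = 64), or 13 after losses. Section 6.1 gives eighty participants; 64 is used because the synopsis and sections 5 and 8.2 agree on it. The result hardly depends on this.
- Correlation ρ between post-test and near-transfer scores: not given; 0 to 0.9 assumed.
- Equal variances, and one score per student per test (the two sutures combined): assumed.
- Students independent: assumed first, then relaxed.

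**Step 1: how the two tests are related.** With one score on each of two occasions, the condition-by-test interaction is the t-test on the change score D = Y₂ − Y₁. With unit variances, cov(Y₂, D) = 1 − ρ and var(D) = 2(1 − ρ). The two test statistics therefore correlate at

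(1 − ρ) / √[2(1 − ρ)] = √[(1 − ρ)/2].

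At ρ = 0.5 this is √0.25 = 0.5. The tests overlap but are far from identical.

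**Step 2: null rejection rate if either counts.** The ceiling for two independent 5% tests is 1 − 0.95² = 9.75%. The large-sample column uses the bivariate normal distribution. The others are simulations of 100,000 null trials per setting, with no effect at either test.

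| ρ | Large sample, either of two | 16 per arm, either of two | 13 per arm, either of two | 16 per arm, post-test-adjusted model added | 13 per arm, post-test-adjusted model added |
|---|---|---|---|---|---|
| 0 | 8.3% | 8.5% | 8.4% | 8.9% | 8.9% |
| 0.3 | 8.8% | 8.8% | 8.7% | 9.1% | 9.0% |
| 0.5 | 9.1% | 9.2% | 9.2% | 9.7% | 9.7% |
| 0.7 | 9.4% | 9.5% | 9.4% | 10.1% | 10.1% |
| 0.9 | 9.6% | 9.6% | 9.6% | 10.3% | 10.4% |

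Each test alone rejects in 4.9% to 5.2% of null trials.

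**Step 3: where the excess comes from.** At 16 per arm and ρ = 0.5, going from one test to two adds 9.16 − 4.96 = 4.2 points. Admitting the adjusted model adds 9.66 − 9.16 = 0.5 points. Across all settings the third route adds about 0.3 to 0.7 points. Choosing a model on fit was not simulated, because the text does not say what the alternatives are.

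**Step 4: other decision rules.** If both tests had to be significant, the rate would be P(t) + P(interaction) − P(either). At 16 per arm this is 5.02 + 5.17 − 8.47 = 1.7% at ρ = 0 and 5.01 + 4.94 − 9.58 = 0.4% at ρ = 0.9. If success meant a significant interaction without a significant post-test difference, it would be 3.5% to 4.6%.

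**Step 5: teaching groups.** Near transfer has two groups of eight per condition. The results below are for 16 per arm and ρ = 0.5, with an assumed intraclass correlation and an analysis that ignores grouping.

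| Intraclass correlation | t-test alone | Either of two |
|---|---|---|
| 0.05 | 9.3% | 16.4% |
| 0.10 | 13.6% | 23.6% |
| 0.20 | 22.0% | 36.4% |

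**The case against.** The strongest reply is that 8.1 contains no either-test rule. The one pattern it describes is joint, namely an interaction with a difference at near transfer and none at post-test, and a joint rule would keep the rate below 5% (step 4). This stands. A reader might infer that near transfer has a false-positive rate of 9-10% instead of 5%. The documents do not support that as a fact: it needs a success rule the plan neither states nor excludes, and the two tests reach 9% only from a correlation of about 0.5, which the plan does not give.

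A reader might also blame the model-fit clause for the inflation. Step 3 shows otherwise. Nor can one say that choosing on fit adds nothing: that holds for one score per occasion, but with two sutures per test and a repeated-measures analysis, covariance structure could have a real role.

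It is also fair that the interaction matches the fourth listed measure, so it is an openly planned analysis. The 8-10% is then a family-wise rate across two quantities, under no effect at either test. But section 4 does not list change from post-test among the outcomes, and 8.1 does not separate it from the near-transfer claim.

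Finally, near transfer is secondary and predicted to be similar or only slightly better under DD. That limits the severity. It does not settle which analysis decides.

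**Conclusion.** The point holds in this form: section 8.1 plans two unranked analyses for one declared secondary outcome, they estimate different quantities, and the model for the second may be settled after the data are seen. If significance on either counted, the null rejection rate would be about 8-10%, or slightly above 10% at high correlation with the post-test-adjusted model added. This rests on an assumed correlation of 0 to 0.9, two-sided 5% tests, 13 or 16 per arm, one combined score per test and independent students. The last assumption does not fit allocation by teaching group; ignoring the groups would raise both the single-test and the either-test rate. The ambiguity about which question is answered needs none of these assumptions. The plan should be changed, but the primary far-transfer comparison is not affected by this point.

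**What to change.** In section 8.1:

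1. Name the DD v IP difference in near-transfer score, the section 4 outcome, as the one deciding near-transfer analysis. Do not adjust for the post-test: it is measured after the teaching, so adjustment changes the question.
2. Estimate it from one pre-specified linear model that averages the two sutures per student, or includes attempt as a repeated measure, and has a term for teaching group. Report a 95% confidence interval. The group term must be written in, since no analysis in 8.1 has one. It should be random, because fixed group effects would absorb the condition effect.
3. From "repeated MANOVA or similar depending on model fit and sampling adequacy", delete everything after the name of the model.
4. Keep the interaction, as the fourth listed measure, as a separately labelled supportive analysis.
5. Reconcile the hypothesis numbering in 8.1 with sections 3 and 5.

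This takes a few sentences and no new data. The analysts can no longer rely on the interaction or the adjusted model, which may have more power when the scores correlate strongly. For the change score, var(D) = 2(1 − ρ) falls below 1 when ρ exceeds 0.5. With four near-transfer groups and two conditions, the group term leaves 4 − 2 = 2 degrees of freedom for the between-group comparison, so the interval will be wide. That reflects allocation by group and is better shown than hidden.

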In a pilot-study completed by our research-partners at the Wilson-Centre in Toronto, Canada, they compared groups of *discovery followed by direct discovery* (DD) with *instruction followed by discovery* (IP). In the case of DD, the participants, where given the materials needed to complete a simple suture, and a finished suture to look at. After the discovery-phase, they were parred with an instructor who demonstrated how it was to be performed. In the IP-case they were first instructed on how to perform the suture, and were afterwards allowed to practice it. At the end of the course both groups were given a post-test of ability, and a week-later both groups were given a retention test as well as a transfer test. The pilot-study included 26 participants in total, divided in two groups of 13. The participants were randomized, and everything was filmed and scored by blinded raters after an international standard. There were no significant results for the immediate post-test as well as the retention test. But in the case of the transfer test, the DD-group was far superior.

Our study will expand on the pilot-study to provide a comparison of guided discovery to traditional instruction for the learning of suturing tasks in surgery, seeing if Guided-discovery-learning works in a much larger research group. Using a double randomized, mixed-methods experimental design, we will investigate the effect of discovery followed by direct instruction (DD) vs. instruction followed by practice (IP) for the acquisition and two types of transfer of surgical skills. To understand *how* and *why* guided-discovery learning changes the learning processes of trainees, we will also film and analyze the interactions of a small-subset of participants in each condition as well as conducting focus-group interviews. Using an exploratory approach, we will explore how discovery learning prior to direct instruction might

change participants' interactions with instructors and task compared to their interactions during initial direct instruction. We will seek to uncover which exploratory approach or approaches provide the best qualitative data. This part is elaborated and investigated in a separate additional protocol.

We hypothesize that:

- 1) Participants in the DD condition will be better able to transfer their knowledge to learning a new skill (i.e., preparation for future learning).

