- 2) Participants in the DD condition will have equivalent performance to IP on post-test, but a similar or slightly improved performance on transfer of suturing skill to a more complex task (near-transfer).
- 3) Participants in the DD condition will interact differently with instructors and will use their learnings from the discovery phase to scaffold their learning during the direct instruction phase as well as interacting differently with the task at hand.

PERSPECTIVES

Faculty instructors are a limited resource in formal simulation-based training during post-graduate training. The rise of structured learning activities such as surgical boot camps and the emphasis on greater feedback and support for trainees means that instructor time is at a greater premium than ever before. Instructors must take time away from their busy clinical and workplace-based education activities in order to teach. Not only does this cost the healthcare system, the time commitment can reduce willingness to participate in education. Additional costs may be incurred by programs that must offer financial incentives for instructors. This trade-off between education and clinical work occurs in all academic postgraduate programs. Given the cost and investment required to recruit faculty for training, research is needed to maximize the efficiency of faculty involvement¹³. Our work directly contributes to this goal by identifying how instructor guidance is most helpful to trainees. Guided-discovery may be one approach to reducing the cost of training and instructor time in both post-graduate as well as pre-graduate learning courses¹⁸.

Post-graduate training also requires that trainees develop autonomy and are able to learn new skills or concepts effectively (Scholar role; Competency 1, Enabling 1.1, 1.2)^{19,20}. Further, Medical Expert^{19,20} (Competency 3, Enabling 3.1, 3.4) stresses trainees' abilities to transfer their training when faced with uncertainty and or complexity in future scenarios. Guided-discovery may be an effective organizing principle for educational design that can achieve these competencies across a wide range of disciplines and training environments. Our proposal would thus establish evidence of efficacy for guided-discovery for these competency roles.

4. Objective and Outcome Measure

Objective	Outcome measure

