6.1 Study Participants

Participants will be students primarily at the Medical Faculty of Copenhagen University who haven't received surgical education yet. Eighty participants will be included split into two groups. Both groups will be taught, filmed and tested at CAMES.

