7.3 Randomization

Randomization

The study is a double randomized study. Participants will be randomized using en-bloc randomization sequence in groups. After enrollment participants will be assigned a group and a date for teaching. And the groups will then be randomized, and assigned a teaching method, which will be revealed on the date of teaching. Each group will then again be randomized to either to a near-transfer or a far-transfer group for the second phase of the study.

Groups range from A through H, making 8 groups in total. All groups assigned an uneven number will be allocated the intervention, whereas groups assigned an even number will be allocated the control. Furthermore, the 4 groups in the control and the intervention will be randomly assigned to a new number. Groups assigned an uneven number will be allocated the near-transfer group, and groups assigned an even number will be allocated the far transfer group.

For the recording and rating of the test each participant will assigned an identification number (A_1, B_1 etc) which will correspond to an identification key-number in the video (eg. 18920, 32, 564). The conversion key will be stored by the principle investigator and only he will have access to it, thus allowing the raters to score the participants blinded.

All randomization will be done using www.random.org and disclosed by an external party.

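### Hypothesis 2 predicts equivalent post-test performance, but section 8.1 plans only difference tests with no margin, and neither a non-significant post-test nor the expected interaction can show equivalence

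*Combined protocol and SAP*

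**What the plan says.** - **Prediction.** Hypothesis 2, at the end of section 3 (Background and Rationale), states: "Participants in the DD condition will have equivalent performance to IP on post-test". For near-transfer it predicts a result that is similar or slightly better.
- **Outcome.** Section 4 makes the post-test a secondary outcome, measured as "Difference in OSATS-scores between immediate post-test".
- **Analysis.** Section 8.1 lists the post-test among its between-group differences, for which "students t-test will be used". It then describes a joint model of post-test and near-transfer scores, "with the expectation of a significant interaction indicating differences between groups at near-transfer but not on post-test".
- **Labels.** Section 8.1 presents that joint model as the analysis for hypothesis 1 and the vertical mattress suture as the analysis for hypothesis 2. Sections 3 and 5 assign them the other way round.
- **Earlier evidence.** For the 26-person pilot, section 3 reports: "There were no significant results for the immediate post-test as well as the retention test".
- **Allocation.** Section 7.3 first places students in eight groups (A to H), and then: "And the groups will then be randomized, and assigned a teaching method, which will be revealed on the date of teaching".
- **Size.** Sections 1, 5 and 8.2 plan 64 students; section 6.1 says "Eighty participants will be included split into two groups".

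Neither the protocol text nor the statistical section gives an equivalence margin, a two one-sided tests procedure, a non-inferiority test or a confidence-interval rule.

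**The concern.** A prediction of equivalence needs a margin and an interval that lies inside it. A difference test supplies neither: a non-significant result may mean the arms are alike, or only that the study was too small to separate them.

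The interaction does not fill the gap, because it contrasts two differences. A positive interaction can arise because DD did better at near-transfer, because DD did worse at post-test, or both. Hypothesis 2 also allows near-transfer to be merely similar, so it could be true with no interaction at all.

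At stake is whether discovery-first teaching costs initial learning. Section 3 presents guided discovery as a possible way to save instructor time, so educators will want to know that cost. If the post-test were reported as equivalent on a non-significant result, the statement would be unsupported and a moderate cost could go unseen.

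**Working it through.** **Inputs from the documents.** Eight teaching groups of eight, four per condition (5, 7.3). All students take the post-test, so 32 v 32. Half the groups in each condition take near-transfer, so 16 v 16. Alpha is 0.05 (8.2), taken as two-sided. The pilot had 13 v 13 (3).

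**Assumptions.** The documents give no OSATS SD, intraclass correlation (ICC) or between-test correlation. Effects are therefore in SD units, ICC is taken as 0, 0.05 and 0.10, and the correlation as 0.5. A single instructor ("We will recruit one 2nd year post-graduate surgical trainees to serve as an instructor") and the script in Appendix A argue for a low ICC, which is why 0 is included.

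**The plan's own figure.** Section 8.2 gives 13 per group, raised to 16, for detecting a large effect. The effect size is cut off in the available text, so 13 cannot be strictly reproduced. Solving back at 80% power gives g of 1.10 (normal) or 1.15 (t) two-sided, and 0.98 or 1.00 one-sided. In every case it is a calculation for detecting a difference, not for showing equivalence.

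**1. How often is a real post-test difference non-significant?**

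Individual level: SE = √(2/n), noncentral t with 2n − 2 df. At n = 32, SE = 0.25 SD and the 95% CI half-width is 0.50 SD.

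Group means: variance of one mean = ICC + (1 − ICC)/8, that is 0.125, 0.169 and 0.2125 for the three ICCs. SE = √(2 × variance/4) = 0.250, 0.290 and 0.326 SD, with 6 df.

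| Analysis | True 0.5 SD missed | True 0.8 SD missed |
|---|---|---|
| 32 v 32, unclustered | 50% | 12% |
| 8 group means, ICC 0 | 61% | 24% |
| 8 group means, ICC 0.05 | 69% | 37% |
| 8 group means, ICC 0.10 | 75% | 46% |
| 40 v 40, unclustered (section 6.1) | 40% | 6% |
| 8 group means of 10, ICC 0 to 0.10 | 53% to 72% | 16% to 42% |
| Pilot, 13 v 13 | 77% | 50% |

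The pilot's 95% CI half-width would be about 0.81 SD, so its null post-test says little about equivalence.

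**2. What does the interaction measure?**

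Interaction = (near-transfer difference) − (post-test difference). On change scores its standardised size is this quantity divided by √(2(1 − ρ)), which is 1 at ρ = 0.5, with 16 v 16.

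Take a near-transfer benefit of 0.5 SD before any carry-over and a DD post-test deficit of 0 or 0.5 SD. If a share c of the deficit persists to near-transfer, the interaction is (0.5 − 0.5c) + 0.5 = 1.0 − 0.5c. Results for 64 students and ICC 0 (simulation, 200,000 runs; the post-test is the 32 v 32 t-test):

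| Truth | Interaction (SD) | Interaction significant | Also post-test non-significant |
|---|---|---|---|
| Post-tests equal | 0.50 | 28% | 26% |
| DD 0.5 SD worse, no carry-over | 1.00 | 78% | 35% |
| DD 0.5 SD worse, half carry-over | 0.75 | 54% | 21% |
| DD 0.5 SD worse, full carry-over | 0.50 | 28% | 9% |

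A deficit that does not fully carry over makes the interaction more likely; with full carry-over it changes nothing. In no row does a significant interaction indicate that the post-tests were equal.

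**3. Could the trial show equivalence?**

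Rule: the 90% CI from the group means lies inside the margin, with the true difference zero. For ICC 0, 0.05 and 0.10, power is 22%, 12% and 7% at a 0.5 SD margin, and 76%, 58% and 43% at 0.8 SD. The margins are assumptions.

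**The case against.** **The word is informal.** It stands in a hypothesis in the background section, beside a loose near-transfer prediction. Sections 4 and 8.1 define the outcome as a difference, which a t-test fits. A reader might infer that the investigators will call p > 0.05 equivalence; the plan does not say so. What stands is that, with no margin or interval rule, nothing else in the plan could support the stated prediction.

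**Carry-over.** Near-transfer uses the same stitch a week later, so a post-test deficit could well persist. A reader might infer that the hoped-for pattern (significant interaction, non-significant post-test) is about as likely under a moderate DD deficit as under true equality. That holds only if little of the deficit carries over. With half or full carry-over the pattern favours equality (26% v 21% or 9%). Nor is a large benefit always needed for it to do so: with 80 students, no carry-over and a 0.6 SD benefit it is 43% v 35%. This objection succeeds against the stronger reading. It does not make the interaction a test of equivalence.

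**Other tests give some protection.** The separate post-test t-test usually detects a large deficit (88% power at 0.8 SD, unclustered). If a significant near-transfer difference is also required, the no-carry-over pattern falls from 26% v 35% to 13% v 16%. This lowers the risk of a misleading result, but still does not demonstrate equivalence.

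**Clustering is wider than this point.** That is so, and the other endpoints are a separate issue. It enters here only because a new interval is proposed, which should reflect the units allocated to a teaching method. An individual-level 95% CI would cover 91% of the time at ICC 0.05 and 86% at 0.10.

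**Conclusion.** The mismatch is real. Hypothesis 2 predicts equivalence, the plan offers only difference tests without a margin, and a true 0.5 SD post-test difference would be missed at least half the time with 64 students. The interaction cannot rescue the claim, since any DD deficit that does not fully carry over makes it larger. The swapped hypothesis labels in 8.1 are a plain inconsistency with sections 3 and 5.

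The absence of a margin and the algebra of the interaction rest on the documents alone. The percentages rest on the assumed effects, ICC and correlation, and those for the interaction also on the assumed carry-over.

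A reader might infer that the main result is at risk. It is not: this is a secondary outcome, and the primary far-transfer comparison does not depend on it. The plan should be changed, but the matter is one of interpretation and reporting.

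**What to change.** 1. **Section 3, Hypothesis 2.** Replace the post-test clause with: *The DD–IP difference on post-test will be estimated; equivalence is not claimed.* Leave the near-transfer prediction as it is.
2. **Section 8.1.** Delete the closing four words of the interaction sentence, which rule out a post-test difference, and add: *The DD–IP post-test difference will be reported in OSATS points with its 95% CI, calculated from the 8 teaching-group means (t, 6 df). Neither a non-significant post-test result nor a significant interaction will be reported as evidence of equivalence.*
3. **Any equivalence claim.** Allow it only if a justified OSATS margin is fixed before any post-test scores are available and the 90% CI from the group means lies inside that margin.
4. **Labels in section 8.1.** Assign the post-test and near-transfer analysis to Hypothesis 2 and the vertical mattress suture to Hypothesis 1.

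**Cost.** Wording and one interval; no new data. With 64 students the 95% CI half-width rises from about 0.50 SD at individual level to a mean of 0.587, 0.682 or 0.765 SD on group means (ICC 0, 0.05, 0.10). The investigators should accept that equivalence probably cannot be shown at this size.
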